Epoch	The planned stage of the subjects' participation in the study. Each epoch serves a purpose in the study as a whole. Typical epochs are: determination of subject eligibility, wash-out of previous treatments, exposure of subject to treatment or to follow-up on subjects after treatment has ended.
Investigational drug	The drug whose properties are being tested in the study; this definition is consistent with US CFR 21 Section 312.3 and is synonymous with "investigational new drug" or "investigational medicinal product."
Investigational treatment	All investigational drug(s) whose properties are being tested in the study as well as their associated treatment controls. This includes any placebos, any active controls, as well as approved drugs used outside of their indication/approved dosage or tested in a fixed combination. Investigational treatment generally does not include other treatments administered as concomitant background therapy required or allowed by the protocol when used within approved indication/dosage
Medication number	A unique identifier on the label of each investigational/study drug package in studies that dispense medication using an IRT system
Subject Number	A number assigned to each patient who enrolls into the study
Part	A subdivision of a single protocol into major design components. These parts often are independent of each other and have different populations or objectives. For example, a single dose design, a multiple dose design that are combined into one protocol, or the same design with different patient populations in each part.
Period	A subdivision of a cross-over study
Premature patient withdrawal	Point/time when the patient exits from the study prior to the planned completion of all investigational/study treatment administration and all assessments (including follow-up)
Randomization number	A unique identifier assigned to each randomized patient, corresponding to a specific treatment arm assignment
Rebound	A subject experiences a rebound, if PASI increases to > 125% of baseline PASI, or if new pustular psoriasis, or new erythrodermic psoriasis, or more inflammatory psoriasis occurs within 8 weeks after the last dose of study treatment has been received.

Stop study participation	Point/time at which the patient came in for a final evaluation visit or when study/investigational treatment was discontinued whichever is later

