Retreatment at start of relapse regimen – “SoR” “start of relapse”: either 150 or 300 mg s.c. secukinumab in PFS: “Start of relapse” will be defined as a loss of $\geq 20\%$ of the maximum PASI gain achieved during the CAIN457A2304 or CAIN457A2304E1 study, compared to baseline of the CAIN457A2304 study, *and* a loss of PASI 75 response. Whenever a subject fulfills the start of relapse criteria, active secukinumab will be administered at their scheduled visits (i.e., every four weeks) until the subject is back to PASI 75 response, at which point in time they will start receiving placebo again. The dose administered in the treatment period of this extension study (secukinumab 150 mg or 300 mg in PFS) will be identical to the dose that these subjects received during the maintenance period of the CAIN457A2304 core study. If a subject does not fulfill the criteria of a start of relapse or is back to PASI 75 response after a start of relapse, they will receive placebo PFS injections (two injections per dose) to maintain the blind. This treatment regimen is applied every four weeks, from Week 52 up to and including Week 152.

At Week 156, patients from the maintenance period of the CAIN457A2304 core study will be unblinded and continue in the study on one of the treatment options in [Table 5-1](#) according to investigator judgment for their assigned treatment arm.

Table 5-1 Open-label treatment options starting at Week 156

Previous treatment arm through Week 152 (Unblinded at Week 156)	Treatment options, as decided by the investigator	New office visit frequency
Secukinumab 300 mg FI	Continue secukinumab 300 mg FI	Every 12-16 weeks
Secukinumab 300 mg SoR	Continue secukinumab 300 mg SoR for remainder of the study OR Switch to secukinumab 300 mg dosed every 4 weeks	Every 4 weeks Every 12-16 weeks
Secukinumab 150 mg FI	Continue secukinumab 150 mg FI OR Switch to secukinumab 300 mg dosed every 4 weeks	Every 12-16 weeks Every 12-16 weeks
Secukinumab 150 mg SoR	Continue secukinumab 150 mg SoR for remainder of the study OR Switch to secukinumab 300 mg dosed every 4 weeks	Every 4 weeks Every 12-16 weeks

Open-label treatment arm for subjects entering from the CAIN457A2307 core study

Secukinumab 300 mg s.c. in PFS regimen arm: Each subject to continue receiving two s.c. injections of 150 mg secukinumab in PFS every four weeks. Doses will be administered from Week 52 up to and including Week 256.

Overview of treatment schedule according to treatment arm

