The treatment details for each treatment arm for Week 52 through Week 152 are highlighted in [Table 5-2](#) below. The treatment details for each treatment assignment for Week 156 through Week 256 are highlighted in [Table 5-3](#) below.

Table 5-2 Overview of treatment between Week 52 and Week 152

Treatment arm	Double-blinded A2304 subjects: Week 52 to Week 152	Open-label A2307 subjects: Week 52 to Week 152
secukinumab 150 mg fixed interval	1 s.c. secukinumab 150 mg PFS injection + 1 s.c. PBO secukinumab PFS injection	N/A
secukinumab 300 mg fixed interval	2 s.c. secukinumab 150 mg PFS injections	2 s.c. secukinumab 150 mg PFS injections
secukinumab 150 mg at start of relapse	At start of relapse and until PASI 75 is regained: 1 s.c. secukinumab 150 mg PFS injection + 1 s.c. PBO secukinumab PFS injection	N/A
	Otherwise: 2 s.c. PBO secukinumab PFS injections	N/A
secukinumab 300 mg at start of relapse	At start of relapse and until PASI 75 is regained: 2 s.c. secukinumab 150 mg PFS injections	N/A
	Otherwise: 2 s.c. PBO secukinumab PFS injections	N/A

PBO = placebo; PFS=pre-filled syringe

Table 5-3 Overview of treatment between Week 156 and Week 256

Assigned treatment	Treatment delivered and frequency of office visits
secukinumab 150 mg fixed interval	1 s.c. secukinumab 150 mg PFS injection every four weeks Office visits required every 12-16 weeks
secukinumab 300 mg fixed interval/ every four weeks	2 s.c. secukinumab 150 mg PFS injections every four weeks Office visits required every 12-16 weeks
secukinumab 150 mg at start of relapse	1 s.c. secukinumab 150 mg PFS injection every four weeks upon meeting SoR criteria and until PASI 75 is regained; no treatment otherwise Office visits required every 4 weeks
secukinumab 300 mg at start of relapse	2 s.c. secukinumab 150 mg PFS injection every four weeks upon meeting SoR criteria and until PASI 75 is regained No treatment otherwise

Assigned treatment	Treatment delivered and frequency of office visits
	Office visits required every 4 weeks

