For subjects willing to self-inject, the first use at enrollment visit (Week 52) will take place under guidance and the supervision of one site staff member. At the enrollment visit (Week 52) the site staff will walk subjects through the “Instructions For Use” on how to self-inject via PFS. At the following visits, subjects will receive the PFS and instructions at the study site to follow on their own.

NOTE: The needle cover of the syringe contains dry rubber (latex), which should not be handled by persons sensitive to this substance.

During the treatment period from Week 52 until Week 256, subjects will receive a maximum of 104 study treatment injections (2 injections of secukinumab 150 mg PFS and/or placebo PFS at each visit). The actual number of study treatment injections will depend on the treatment assigned. All subjects will receive 52 study treatment injections between Week 52 and Week 152 (2 injections of secukinumab 150 mg PFS and/or placebo PFS at each visit); between Week 156 and 256 subjects could receive as many as 52 study treatment injections (2 injections of secukinumab 150 mg PFS every four weeks) or as few as 0 study treatment injections (SoR treated subjects who do not meet start of relapse criteria at any point).

At study visits when pre-dose blood samples have to be drawn ([Table 6-1](#)), the study treatment will be injected to the subject only after the blood samples have been taken.

At each visit, all study assessments, including the completion of Patient Reported Outcomes (PROs), should be completed prior to the self injection of study treatment.

After Week 256, no further study treatment will be administered during the treatment period. In addition, no study treatment is administered during the follow-up period and follow-up 2 period.

The subject should be instructed to contact the investigator if he/she is unable for any reason to attend a study visit as scheduled.

All dates, times of injections, mode of injection (self or by study site staff) during the study must be recorded on the Dosage Administration Record eCRF. Immediately before dispensing the package for injection, investigator staff will detach the outer part of the label from the packaging and affix it to the source document (Drug Label Form) for that subject's unique subject number.

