9.5 Analysis of secondary variables

9.5.1 Efficacy variables

Maintenance of response

Maintenance of response will be defined analogously as in the primary endpoint in CAIN457A2304, but for week 104 and 156, i.e. PASI 75 response

- at Weeks 104 and 156, for subjects in the fixed interval regimens, or
- at Weeks 92 and 144, for subjects in the retreatment at start of relapse regimen who do not require active treatment at Week 92 or 144, respectively, or
- at Weeks 104 and 156, for subjects in the retreatment at start of relapse regimen who do require active treatment at Week 92 or 144, respectively.

Summary statistics for maintenance of response at Week 104 and 156 will be presented in contingency tables and will include absolute and relative frequencies. Confidence intervals for response rates will be derived as well based on the score method including continuity correction ([Newcombe 1998](#)).

PASI 50, PASI 75, PASI 90, PASI 100 and IGA 0 or 1 response over time

Summary statistics for PASI 50, PASI 75, PASI 90, PASI 100 and IGA 0 or 1 response by visit will be presented in contingency tables and will include absolute and relative frequencies. Confidence intervals for response rates will be derived as well based on the score method including continuity correction ([Newcombe, 1998](#)).

PASI score over time

Summary statistics will be provided for absolute PASI scores as well as for percent change from baseline by visit and treatment group. Figures will also be provided.

IGA mod 2011 score over time

Summary statistics for the IGA mod 2011 score over time will be presented by visit and treatment group in contingency tables.

Relapse

The number and percentage of subjects experiencing relapse will be presented by visit and treatment group.

Rebound

Rebound is defined as a worsening of PASI of > 125% of the value at baseline (core study), or new pustular, erythrodermic or more inflammatory psoriasis occurring within 8 weeks of stopping therapy (i.e., if this definition is fulfilled at more than 8 weeks after last study treatment administration, this is not defined as rebound). The number and percentage of subjects experiencing rebound will be presented by visit and treatment group.

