### **1.6 Study medication**

The analysis of study treatment data will be based on the safety set.

The number of planned and actual injection number will be summarized by yearly interval (analysis visit) for entire treatment period and treatment group AIN457 150 mg FI and AIN457 300 mg FI.

In case it cannot be identified from the data collected or assumed from the planned treatment whether an injection contained placebo or secukinumab, it will be assumed that the syringe contained secukinumab. For example this applies to the 150 mg secukinumab treatment group (in which subjects should receive both an active and a placebo injection) if only one injection is given. If the medication pack number is not available, it will be assumed that the secukinumab injection was applied. If this scenario occurs for subjects in the 300 mg treatment group when subjects should receive two identical injections, it will be assumed that they received secukinumab as planned.

The duration of exposure to study drug will be summarized by treatment group and yearly interval for entire treatment period.

Duration of exposure will be defined and summarized as follows:

For extension study period, duration of exposure will be defined as the time from first dose of study medication in extension 1 to the end of treatment period in extension 1 study; and for entire study period duration of exposure will be defined as the time from first dose of study medication in core study to the end of treatment period in extension 1 study. The end of treatment period will be defined as the last dose plus 84 days or last visit whichever occurs earlier. i.e., for subjects who discontinued or have their last visit earlier than last dose plus 84 days, the end of study treatment exposure will be the date of the last study visit in the corresponding treatment period.

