## **1.8 Efficacy evaluation**

### **1.8.1 Variables**

The primary objective of the study is to assess long-term safety and tolerability of secukinumab in subjects with moderate to severe chronic plaque-type psoriasis who completed treatment in the core studies CAIN457A2304 and CAIN457A2307.

The analysis of the secondary efficacy variables will be based on the FAS.

The main secondary efficacy analysis is maintenance of response. Maintenance of response is defined as follows:

- for subjects in the fixed interval regimens, maintenance of response is defined as PASI 75 response at Weeks 104 and 156
- for subjects in the start of relapse regimens maintenance of response is defined as

- PASI 75 response at Weeks 92 and 144 for subjects who do not require active treatment at Week 92 or 144 and
- PASI 75 response at Weeks 104 and 156 for subjects who do require active treatment at Week 92 or 144.

In order to identify whether active treatment was applied at Weeks 92 and 144 the following will be utilized:

- Visit windows as in Table 1-8 (as for efficacy with date of randomization as day 1) will be applied to dosing date.
- The analysis visit Weeks 92 and 144 will be identified for dosing. The PASI assessment for the corresponding CRF visit will be selected.
- If no dosing for analysis visit Weeks 92 and 144 is identified, it is concluded that no active treatment was given. Therefore, the PASI 75 response status of the analysis visit Weeks 92 and 144 will be considered.
- For subjects with assigned dosing records at Weeks 92 and 144 but for which no corresponding PASI assessment can be assigned, non-responder imputation will be performed

Apply visit windowing to the dosing dates then find the weeks 92 and 144 dosing date. With this dosing date search for the corresponding PASI data with the same date. If there was no AIN dosing at these weeks 92 and 144 then it shall be assumed that the PASI response at Weeks 92 and 144 will be taken for the maintenance of response parameter.

[Table 1-10](#) lists the variables for the final analysis.

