### **Rebound or rebound like events**

The number and percentage of subjects experiencing rebound or rebound like events will be presented by treatment group as follows:

[figure not shown]
- For rebound, all assessments done up to 8 weeks after last injection will be summarized.
- Similarly for rebound like events, all assessments done up to 12 weeks after last injection will be summarized.

Subjects who received commercially available Cosentyx® will be excluded from this analysis.

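### Rebound is counted from the last injection, which for start-of-relapse subjects who stop before Week 156 can be a placebo injection given long after active drug ended

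*SAP*

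**What the plan says.** The SAP, under Rebound or rebound like events in 1.8.7, sets the window: "For rebound, all assessments done up to 8 weeks after last injection will be summarized". Rebound-like events get 12 weeks from the same starting point; the protocol has no such category. One figure in that paragraph is not shown. The visible text does not say whether the injection must be active.

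The protocol uses an equivalent anchor. The glossary refers to worsening or "more inflammatory psoriasis occurs within 8 weeks after the last dose of study treatment has been received". Section 9.5.1 speaks of stopping therapy and then explains that "if this definition is fulfilled at more than 8 weeks after last study treatment administration, this is not defined as rebound".

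Both documents treat placebo syringes as injections of study treatment. Protocol 5.5.4 counts "52 study treatment injections between Week 52 and Week 152 (2 injections of secukinumab 150 mg PFS and/or placebo PFS at each visit" for every subject. SAP 1.6 covers the case where it is unclear "whether an injection contained placebo or secukinumab, it will be assumed that the syringe contained secukinumab".

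For the SoR arms, protocol 5.2 says: "Whenever a subject fulfills the start of relapse criteria, active secukinumab will be administered at their scheduled visits". This lasts until PASI 75 is regained; at all other visits to Week 152 they receive two placebo injections. From Week 156 placebo ends, and Table 5-3 gives active drug "upon meeting SoR criteria and until PASI 75 is regained; no treatment otherwise".

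Rebound belongs to a secondary objective (protocol 2.2). SAP Table 1-2 tabulates it by treatment group, with SoR and fixed-interval groups side by side.

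**The concern.** Rebound is meant to describe worsening soon after therapy is withdrawn. The SAP also excludes subjects who received commercial drug, which suggests that it wants to observe time off active secukinumab. In the fixed-interval and open-label groups every dosing visit includes active drug, so 8 weeks after the last injection is 8 weeks off drug. An SoR subject in remission may have had only placebo for many months before stopping. The same rule then opens the window at a placebo injection and can label an ordinary late return of psoriasis as rebound. The percentages in the table would then describe different things in different columns.

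**Working it through.** **Inputs.** Dosing is every 4 weeks from Week 52 to Week 152 in the blinded part (protocol 5.2). Protocol 3.1 puts the end-of-treatment (EOT) assessments of early stoppers about 4 weeks after the last secukinumab or placebo dose, and Section 6 says 4 weeks after the last study treatment; 5.5.9 mentions only secukinumab. The Week 264 and Week 268 visits follow at 4-week steps. Times below are nominal and ignore the ±5-day visit window.

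**The plan's own figures reproduce.** Last dose Week 256: 264 − 256 = 8 weeks and 268 − 256 = 12 weeks, as protocol 3.1 states. Blinded dosing visits: (152 − 52)/4 + 1 = 26, and 26 × 2 = 52 injections, as in 5.5.4.

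**Shift of the window.** Let g be the weeks from the last active dose to the last injection. The three visits fall g + 4, g + 8 and g + 12 weeks after active drug. The SAP 8-week window contains the first two; the 12-week window contains all three.

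| g | Visits, weeks after active drug | Visits in 8-week window within 8 weeks of active drug | Visits in 12-week window within 12 weeks of active drug |
|---|---|---|---|
| 0 | 4, 8, 12 | 2 of 2 | 3 of 3 |
| 4 | 8, 12, 16 | 1 of 2 | 2 of 3 |
| 8 | 12, 16, 20 | 0 of 2 | 1 of 3 |
| 12 | 16, 20, 24 | 0 of 2 | 0 of 3 |
| 20 | 24, 28, 32 | 0 of 2 | 0 of 3 |

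Fixed-interval and open-label subjects always have g = 0. For an SoR subject the 8-week window closes g + 8 weeks after active drug:
- last active dose Week 52, last placebo Week 104: 52 + 8 = 60 weeks;
- last active dose Week 52, last placebo Week 152: 100 + 8 = 108 weeks;
- never retreated, assuming the last active dose was at Week 8 of the core study: 144 + 8 = 152 weeks.

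The issue ends with the Week 152 injection, because no placebo is given after it.

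**What can be counted in that window: the PASI criterion.** Rebound needs PASI above 125% of baseline. Placebo at the last dosing visit means that the SoR criteria (loss of at least 20% of the maximum gain, and loss of PASI 75) were not both met. For a Week 12 PASI 75 responder the maximum gain is at least 75%.
- Maximum gain 75%: improvement still above 0.8 × 75 = 60%, so PASI was below 40% of baseline. The rise needed exceeds 125/40 = 3.1-fold.
- Maximum gain 93.75% or more: 0.8 × 93.75 = 75, so PASI was at most 25% of baseline. The rise needed exceeds 125/25 = 5-fold.

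**What can be counted: the symptom criterion.** New pustular, new erythrodermic or more inflammatory psoriasis is recorded as yes or no (protocol 6.4.2.1) and has no PASI threshold. Table 6-1 schedules the question only at Weeks 260, 264 and 268, plus unscheduled visits in treatment-free follow-up. For an early stopper on placebo it is therefore asked only after the last placebo injection, inside the SAP window.

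**The true 8 weeks after active drug.** With g of 8 or more, the subject received placebo at the visits 4 and 8 weeks after active drug, so the SoR criteria were not met there. PASI above 125% of baseline means that more than 100% of the gain and PASI 75 are lost, which would have triggered active drug. On PASI, then, no rebound was seen at those visits, yet later follow-up visits remain eligible to count.

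**The case against.** The SAP did not invent this anchor. The protocol counts from the last study treatment, and placebo is study treatment; the rule can be read as time since leaving the assigned regimen, applied alike in every arm. That stands, so a reader who infers that the SAP departs from the protocol would be wrong: the gap is in both documents. It does not rescue the measure, because leaving a placebo phase is not withdrawal of active drug.

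The missing figure could hold part of the definition. That stands as a caveat on the visible text.

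The PASI criterion is demanding, so few events may arise from it. That also stands. It leaves the symptom criterion.

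A reader might also infer that the table wrongly omits SoR subjects who worsen after active drug is withheld and are then retreated. The documents do not support this. Those subjects have not stopped therapy, so they lie outside the protocol's definition, and their worsening appears under relapse and PASI over time.

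Counting from active drug leaves SoR subjects with g of 8 or more without a scheduled symptom assessment in the 8-week window. This is a real cost. It shows that rebound was not assessed by symptoms in these subjects, which should be reported openly.

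Finally, the SAP amendment is dated April 2018 and four interim analyses had been done, so a new anchor would come late. That is a reason to keep the protocol-anchored count beside it.

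**Conclusion.** The point holds as a flaw in a definition shared by protocol and SAP. For SoR subjects who stop before Week 156 while on placebo, the 8-week window can lie entirely beyond 8 weeks of active drug: 0 of 2 counted visits qualify once g is 8 or more. A late return of disease, mainly through the symptom question, can then be tabulated as rebound in the SoR groups and in no other group.

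The number of subjects or events affected is not in the documents. A reader might try to build one from the roughly 108 of 675 subjects who had discontinued at Amendment 1. That figure is not split by arm or by type of last injection, and it would at best count shifted windows, not misclassified events. The effect on the table may be small. No hypothesis is tested (SAP 1.8.3) and the primary objective is safety, so what is at stake is the comparability of one descriptive table for a secondary objective.

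The conclusion assumes that the figure not shown does not restrict the anchor to active injections, and that early stoppers attended at the nominal times. A change is worth making because it is cheap.

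**What to change.** 1. In SAP 1.8.7, count the 8-week and 12-week windows from the last active secukinumab dose in all groups. List this in SAP 1.1.1 as a change from the protocol.
2. Report, by group, how many subjects have no PASI and how many have no symptom assessment in each window.
3. Keep the count from the last injection, active or placebo, as a labelled sensitivity summary.

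No new visits or data are needed. Doses are recorded, medication numbers are held in the IRT, and PASI was scheduled every 4 weeks before Week 156. SAP 1.8.1 already separates active dosing for another endpoint: "In order to identify whether active treatment was applied at Weeks 92 and 144 the following will be utilized". The cost is one revised paragraph, two counts per window and one extra summary. The downsides are that some SoR subjects will have no in-window symptom assessment and that the main definition will differ from the protocol wording.

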Subjects who complete the treatment period (the end of the treatment phase visit is at Week 260) will enter the treatment free follow-up period with the following visits: Week 264 (Follow-up visit 4, F4), which is 4 weeks post end of treatment period and 8 weeks post last dose), and Week 268 (Follow-up visit 8, F8 or End of Follow-up, EOF) which is 8 weeks post end of

treatment period and 12 weeks post last dose). Subjects who prematurely discontinue treatment should complete all assessment of Week 260 (end of treatment visit) and then enter follow-up period with Weeks 264 and 268 visits.

[figure not shown]
Subjects within the follow-up period who withdraw from study should perform Week 268 assessments (EOF).

Follow-up 2 period (only for subjects who prematurely discontinued treatment)

Subjects who have prematurely discontinued treatment prior to the end of treatment phase (Week 260), and completed the Week 260 visit and the subsequent follow-up period visits (Weeks 264 and 268) should enter the treatment-free follow-up 2 period. Follow-up 2 period consists of telephone calls every 3 months and unplanned assessments e.g. unscheduled physical examinations, vital signs and laboratory assessments at the site if investigator considers this necessary. The end of Follow-up 2 period (EOF2) for an individual subject will be after 4 years from the time when subject has been enrolled into the CAIN457A2304E1 study (Figure 3.1).

Subjects within the follow-up 2 period who withdraw from study will be recorded in the End of Follow-up 2 (EOF2) completion eCRF page.

Figure 3-1 Study design

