5.5.12 Early study termination

The study can be terminated at any time for any reason by Novartis. Should this be necessary, the patient should be seen as soon as possible and properly managed for a prematurely withdrawn patient. The investigator may be informed of additional procedures to be followed in order to ensure that adequate consideration is given to the protection of the patient's interests. The investigator will be responsible for informing IRBs and/or ECs of the early termination of the trial.

6 Visit schedule and assessments

[Table 6-1](#) Assessment Schedule lists all of the assessments and indicates with an "x" when the visits are performed.

Subjects should be seen for all visits on the designated day within the allowed “visit window” specified below or as close to it as possible.

During the treatment period, subjects may be seen at an unscheduled visit, e.g. if they experience deterioration of psoriasis, or AEs that in the opinion of the investigator need intervention or repeated laboratory testing. During these unscheduled visits, study treatment will NOT be administered. A visit window of “±5” will be allowed for Week 52 to Week 260 during the treatment period during the follow-up period or as close to it as possible.

Subjects who discontinue study treatment will continue to be followed for safety assessments. They are not considered withdrawn from the study.

Subjects who discontinue study treatment before completing the study, and those who prematurely withdraw from the study for any reason should be scheduled for a study visit 4 weeks after their last study treatment administration, at which time all the assessments listed for EOT (Week 260) will be performed (see [Section 5.5.10](#)). Subjects will return to the study site for further assessments as indicated under the follow-up visits (Weeks 264 and 268) (see [Section 3.1](#)).

Only subjects who prematurely discontinued study treatment should enter follow-up 2 period after completion of follow-up visits (Weeks 264 and 268). Follow-up 2 period includes telephone calls every 3 months until 4 years from the time subjects have been enrolled into CAIN457A2304E1 as well as potential unplanned assessments e.g physical examinations, vital signs and laboratory assessments during this time.

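### The rebound analysis excludes every subject who ever received commercial secukinumab, whatever the start date, and so discards valid drug-free assessments that censoring would keep

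*SAP*

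**What the plan says.** Rebound is part of a secondary objective (Protocol 2.2; SAP 1.1). SAP 1.8.7 sets two observation windows: "For rebound, all assessments done up to 8 weeks after last injection will be summarized", and "Similarly for rebound like events, all assessments done up to 12 weeks after last injection will be summarized". It then adds "Subjects who received commercially available Cosentyx® will be excluded from this analysis". The sentence follows both windows and carries no condition on when the commercial product was started.

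Protocol 9.5.1 defines rebound and plans counts and percentages by visit and treatment group. It has no exclusion for commercial product and no rebound-like category. SAP 1.1.1, which lists departures from the protocol's methods, mentions neither.

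The 8-week limit is the protocol's own. Section 9.5.1 states that "if this definition is fulfilled at more than 8 weeks after last study treatment administration, this is not defined as rebound". Protocol 3.1 places Week 264 at a point "which is 4 weeks post end of treatment period and 8 weeks post last dose".

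On the PASI criterion, the protocol glossary says "if PASI increases to > 125% of baseline PASI", while Protocol 9.5.1 says "a worsening of PASI of > 125% of the value at baseline (core study").

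**The concern.** Drug taken inside the observation window can mask rebound, so commercial use needs some handling. Excluding the whole subject goes further than that. It also removes what was seen while the subject was still off drug, and it removes subjects whose commercial start came after the windows had closed.

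Whether a subject is excluded depends on something that happens after the last study dose and may be related to flare. If it is related, the subjects left are a selected group and the reported rate is biased. If it is not, the analysis still loses usable data. Because SAP 1.1.1 does not declare the exclusion, a reader comparing the report with the protocol would not know that the analysed population had changed.

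**Working it through.** **Inputs.** Scheduled days in SAP Table 1-8: Week 256 (last dose) 1793, Week 260 1821, Week 264 1849, Week 268 1877. Rebound symptoms are assessed at Weeks 260, 264 and 268 (Protocol Table 6-1). Windows: 8 weeks = 56 days and 12 weeks = 84 days (SAP 1.8.7). Maximum PASI: 72 (Protocol 6.4.2).

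**Step 1: reproduce the plan's timing.**
- Week 260: 1821 − 1793 = 28 days (× 24 = 672 hours, as in Protocol Table 15-1).
- Week 264: 1849 − 1793 = 56 days = 8 weeks, as Protocol 3.1 states.
- Week 268: 1877 − 1793 = 84 days (× 24 = 2016 hours, as in Table 15-1).

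**Step 2: planned drug-free assessments kept under each rule.** Start days 40 and 70 are illustrations.

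| Commercial start, days after last injection | Assessments before start | Kept by exclusion | Kept by censoring |
|---|---|---|---|
| Before 28 | none | 0 | 0 |
| 40 | day 28 | 0 | 1 |
| 70 | days 28, 56 | 0 | 2 |
| After 84 (follow-up 2) | days 28, 56, 84 | 0 | 3 |

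The last row matters most. Protocol 5.5.8 bars the treatments in Table 5-4 throughout the study except in follow-up 2. Commercial secukinumab is not named there, but the row for other biological immunomodulating agents would naturally cover it. On that reading, a compliant subject can start it only after Week 268, when both windows have closed. Only subjects who stopped treatment prematurely enter follow-up 2 (Protocol 3.1). For them the exclusion removes complete, valid observation.

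**Step 3: effect on the reported rate.** Let p be the true rebound rate, a the share of rebounders who receive commercial product, and b the share of other subjects who do. After whole-subject exclusion:

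reported rate = p(1 − a) / [p(1 − a) + (1 − p)(1 − b)]

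The documents give none of these values. With p = 0.05 assumed:
- a = 0.5, b = 0.2: 0.025 / (0.025 + 0.760) = 0.025/0.785 = 3.2%.
- a = 0.4, b = 0.2: 0.030 / (0.030 + 0.760) = 0.030/0.790 = 3.8%.
- a = b: 5.0%, so no bias, only fewer subjects.
- a = 0.2, b = 0.5: 0.040 / (0.040 + 0.475) = 0.040/0.515 = 7.8%.

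**Step 4: the Week 264 boundary (secondary).** The nominal visit falls on day 56, so a visit one day late leaves the rebound count and enters the rebound-like count. Protocol Section 6 gives a ±5-day window for Weeks 52 to 260 and then continues "during the treatment period during the follow-up period or as close to it as possible", so it is unclear whether the window covers Week 264. If it does and the last dose is on its nominal day, the visit falls on days 51 to 61, and 5 of those 11 days exceed 56. The share of visits affected is 5/11 = 45% if days are uniform. If days are normal and rounded to whole days, the share is 1 − Φ(0.5/SD): 16%, 31%, 40% and 43% for SDs of 0.5, 1, 2 and 3 days. These spreads are assumptions.

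**Step 5: the PASI wording (secondary).** At baseline PASI 20, the glossary gives 1.25 × 20 = 25. If Section 9.5.1 is taken as the size of the increase, it gives 20 + 1.25 × 20 = 45. That second reading cannot be met at a baseline of 32 or more, because 72/2.25 = 32.

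**The case against.** Subjects may move straight from study drug to the marketed product to continue therapy. They are never off drug, rebound cannot be assessed in them, and leaving them out is sensible. Rebound is also listed among the efficacy variables, is only described, and has no hypothesis test (SAP 1.8.3). The primary safety analysis is untouched. All of this stands. It supports disregarding assessments made after the commercial start, but it does not support deleting those made before it.

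A reader might infer more than the documents support:

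- *The exclusion hides rebound and lowers the rate.* The documents give neither reasons nor timing for commercial use. Step 3 shows that the rate can move either way.
- *Late Week 264 visits are dropped.* They are not. Up to 12 weeks they count as rebound-like, and the 8-week limit is the protocol's definition, which the SAP follows.
- *The protocol contains two incompatible thresholds.* Both wordings can be read as 1.25 times baseline, and the impossibility at high baselines counts against the other reading. This is loose protocol wording.
- *The SAP has no rebound definition.* SAP 1.8.1.1 refers forward to one and none appears in the visible text, but an item in SAP 1.8.7 is not shown and may contain it. No omission can be claimed.

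**Conclusion.** The point holds for the undated exclusion. It is absent from Protocol 9.5.1, is not declared in SAP 1.1.1, and taken literally costs up to three planned drug-free assessments per affected subject. The loss is complete for those who start only in follow-up 2.

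The number of subjects affected and the direction of any bias cannot be derived from the documents. The span of 3.2% to 7.8% around an assumed true 5% is illustrative. The follow-up 2 argument rests on reading Table 5-4 as covering commercial secukinumab. The loss of assessments made before an earlier start does not depend on that reading.

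The change should be made because rebound is a named secondary objective and the remedy is cheap. The Week 264 boundary and the PASI wording are clarifications of lesser weight.

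**What to change.** In SAP 1.8.7, replace the exclusion with a dated rule:

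- Censor each subject at the date of the first commercial dose, and disregard rebound assessments after that date.
- Count rebound and rebound-like events observed before it, within their existing windows.
- State the denominator, and report by treatment group how many subjects were censored within each window and how many had no drug-free assessment before starting.
- Declare the handling of commercial product, and the added rebound-like category, in SAP 1.1.1.

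The start date is already required on the concomitant-medication record (Protocol 5.5.7). SAP 1.7 already provides for imputed dates and for a separate follow-up 2 listing. The cost is slightly more programming, and the reported rate may change. Censoring does not recover what would have happened after a start inside the window, which is why the number censored should be shown.

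For the secondary points, keep the protocol's 8-week count as the main result and, if wanted, add a sensitivity count that includes the Week 264 visit with its tolerance stated. Reconcile the glossary and Protocol 9.5.1 to one PASI threshold, and repeat it in the SAP text.
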